###### **Study design:**

If a patient expresses interest in participating they will be introduced to a member of the research team to discuss the study and complete informed consent. All participation is voluntary and participants are able to withdraw from the study at any point. The study participant will be asked to complete a questionnaire, which was adapted from the previously approved survey ([IRB00122933](#)), which includes the NOSE instrument, questions regarding the patient's current treatments, and a ranking of their preferred characteristics of an ideal nasal dilator (see Appendix A).

Patients will then be asked to inhale rapidly into an airflow transducer to measure baseline peak nasal inspiratory flow (PNIF). Following the pre-test survey participants will be fitted serially with five commercially available nasal dilator products per manufacturer recommendations (Breathe Right strips, Max Air nose cones, Sleep Right dilator, Mute dilator, and Nozovent dilator), and one experimental nasal dilator designed by the research team ("Schnozzle"). In this crossover design study participants will be blinded as to which dilators are branded and which are experimental, and the order of fitting nasal dilators will be randomized. Each subject will undergo PNIF testing for all six devices.

After each fitting and use for five minutes to adjust to the device and confirm there is no immediate discomfort or irritation, participants will undergo repeat PNIF testing with each device and then will be free to go home and trial the devices on their own. Participants will be given a schedule specifying one device to trial for at least one continuous hour per day. This schedule will specify devices in a randomized order,

and participants will continue to be blinded as to which device they will be using on a particular day (Schnozzle, Breathe Right, Max Air, Sleep Right, Mute, and Nozovent). The devices will be numbered in a random fashion, for participants to be able to identify which device via the assigned number they are scheduled to use on that day. They will similarly use the device number when performing any device evaluation.

Participants are free to wear the assigned nasal dilator at their leisure beyond one hour, but must log the hours and activities performed while wearing the device (for example, “10am-11am exercising”). Patients are not required to wear a device in public at work or during exercise unless they feel comfortable doing so. All devices should be worn overnight. When the schnozzle is utilized at night, a modified version will be used where each portion inserted into the nares will be connected by an external bridge. This is to prevent posterior displacement of the device during sleep. Each morning, the participant will complete a survey summarizing their experience using the assigned device (Appendix B). If there is any discomfort, irritation, skin breakdown, or epistaxis the participant should stop wearing the device and contact the research team immediately.

Over the course of the first six days since the initial clinic visit, the participant will trial and log their use of each of the six nasal dilators. After at least six days (one day per device) participants will return to the office for an exit interview with the study team in regards to their subjective experience with each device. At the end of each trial day they will be asked to fill out a concluding survey (see appendix C). At their exit interview they will be asked to submit both appendix B and C for each device they trialed.

Before returning to the clinic for the conclusion of the study, participants may have several days without an assigned device. Participants are free to stop wearing all devices or use any device as they please as long as it is consistent with proper care and use of the device(s).

*b. Study duration and number of study visits required of research participants.*

This study requires two office visits – one to begin the study with baseline PNIF measurements, device fitting, PNIF with each device in place, and a perception survey. This will be followed up with a wrap up visit end the study with a concluding survey. Each patient will participate in the study for at least six days to trial each device, and the entire duration depends on an individual patients’ ability to return to the clinic, no more than two weeks.

Participants will be free to stop participating at any point during the study. Participants will have the option to be included in a list of individuals who would be interested and willing in participating in additional study sessions.

*c. Blinding, including justification for blinding or not blinding the trial, if applicable.*

Patients will be blinded to the names of the devices tested to limit bias when they complete the surveys. They will also be blinded as to which device was designed by members of the research team.

*d. Justification of why participants will not receive routine care or will have current therapy stopped.*

The standard of care is to do nothing, use existing nasal dilator devices, or surgery. This one session comparison study of nasal dilators does not prevent patients from proceeding with the standard of care after the study session, and will familiarize them more thoroughly with available treatment options.

*e. Justification for inclusion of a placebo or non-treatment group.*

Participants will serially wear the prototype Schnozzle device and marketed nasal dilators, all of which are treatments. We will get a baseline NOSE and PNIF score from participants without any assistive devices in place, which serves as the placebo/ non-treatment arm of the study. Following the study session participants can continue to use currently marketed nasal dilators or proceed with planning surgery.

*f. Definition of treatment failure or participant removal criteria.*

Participants will be removed from the study if they experience substantial discomfort with the study devices, or if they experience any adverse events, such as epistaxis, or skin breakdown or if they would like to discontinue testing for any reason.

*g. Description of what happens to participants receiving therapy when study ends or if a participant's participation in the study ends prematurely.*

At the end of the study session participants will be able to continue using any of the marketed nasal dilator products currently on the market, and this study will not influence their ability to proceed with scheduling surgery if indicated and desired. They will not be able to continue using the Schnozzle nasal dilators at this time as it is still in early stage development and not widely produced or available.

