The most common structural pathologies that contribute to nasal obstruction are septal deviation (54%) and internal nasal valve collapse (14%), both of which increase resistance through the internal nasal valve. The internal nasal valve is defined by the junction of the nasal septum, caudal border of the upper lateral cartilage, and head of the inferior turbinate; it contributes to two-thirds of the total nasal resistance. [3] As per Poiseuille's law, resistance increases as a factor of the radius to the fourth power. As such, small changes to the dimensions of the internal nasal valve cause an exponential change in flow. In septal-deviation, the septum- the bony and cartilaginous structure that divides the nasal cavity- is deflected, dislocated off the maxillary crest, or off-center, causing a reduction in cross-sectional area of the internal nasal valve. Valvular collapse occurs when the lateral nasal wall paradoxically moves medially on inspiration at the level of the internal valve, causing a corresponding decrease in cross-sectional area and increase in nasal resistance. The cause of which can be congenital – from weak upper lateral cartilage or lack of dilator function, develop as a result of trauma, or occur post-operatively in patients following nasal surgery [8].

There are a number of over-the-counter consumer products that attempt to relieve this mechanical nasal obstruction in an effort to avoid surgery. One of the most popular external dilators is Breathe Right, a flexible strip that is adhered to the nose and stents the lateral walls of the nose outward to prevent internal nasal valve collapse [8]. Other existing solutions take the form of nasal cones and clips that act intra-nasally to stent the collapsed nasal valve. While studies show that these products are mostly effective in increasing nasal airflow, they are typically described as uncomfortable and carry social stigma due to visibility during use, leaving their use for an extended period of time limited [11].

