## 7. Study Statistics

### a. Primary outcome variable.

Peak Nasal Inspiratory Flow (PNIF) and Nasal Obstruction Symptom Examination (NOSE) score for each individual before the trial and while using each tested nasal dilator.

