## 8. Risks

### a. Medical risks, listing all procedures, their major and minor risks and expected frequency.

Application and wearing of any of the experimental or existing nasal dilators could conceivably lead to:

1. Discomfort, including moderate temporary pain, or irritation, including tickling that may cause sneezing. Discomfort associated with wearing the devices is expected to be uncommon, minor, and self-limited. Participants have the option to refuse or remove any or all of the nasal dilator system at any point.

2. Epistaxis (nose bleeding), is unlikely given that patient with abnormal nasal mucosa are not included in the study. Participants will be trained and assisted by study personnel to atraumatically apply and remove the nasal dilator devices. Should a participant experience epistaxis they will be managed according to the standard of care, which would involve application of manual pressure to the cartilaginous portion of the nose for 20 minutes. Should bleeding be severe or persistent they will be seen by an Otolaryngologist for further management and treatment.

3. Migration of nasal dilator device is highly unlikely given the pre-clinical testing of nasal dilators in a nose model under extreme conditions of high airflow that could be associated with sneezing and peak inspiratory breathing. Additionally, the normal nasal anatomy, namely the inferior nasal turbinates, limit the open space in the nose and should prevent migration of nasal dilators. Individuals with markedly abnormal inferior turbinates are excluded from this study.

4. Nasal dilators may be ineffective at improving nasal airflow during the study. These subjects will not be excluded but may leave the study.

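### The plan expects a PNIF reading on all six devices from everyone but allows devices to be refused and participants to be removed, and section 7c does not say how the resulting gaps are analysed

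*Combined protocol and SAP*

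**What the plan says.** - **Intended data.** Section 7a makes PNIF, together with NOSE, the primary outcome for each person at baseline and "while using each tested nasal dilator". Section 4a (Study design) states: "Each subject will undergo PNIF testing for all six devices".
- **Timing.** The reading with a device comes "After each fitting and use for five minutes to adjust to the device and confirm there is no immediate discomfort or irritation".
- **Loss of one device.** Section 8a, item 1: "Participants have the option to refuse or remove any or all of the nasal dilator system at any point".
- **Loss of the participant.** Section 4f: "Participants will be removed from the study if they experience substantial discomfort with the study devices". The same section removes people for adverse events such as a nosebleed or skin breakdown.
- **Expected frequency.** Section 8a, item 1: "Discomfort associated with wearing the devices is expected to be uncommon, minor, and self-limited". No percentage is given.
- **Analysis.** Section 7c offers ANOVA at p < 0.05, and only if a statistical evaluation is pursued. It does not state the form of the ANOVA, the analysis set or a rule for missing readings. It plans 35 people per cohort and expects to lose 5 from each.

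**The concern.** The plan assumes a full grid of unaided PNIF plus six device readings per person, yet describes two routes that leave holes in it. A refused device gives no reading with that device in place. A participant removed during the session also loses every device still to come in the random order.

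What follows depends on a choice that section 7c leaves open:

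- **Complete rows.** A conventional repeated-measures ANOVA keeps only people with every cell filled. One missing device then discards that person's valid readings on the other devices and the unaided reading. Six devices multiply a small per-device loss.
- **Available cases.** Each device's mean comes from whoever has a reading on it. The means may then describe somewhat different people, selected by what they tolerated. Random order does not cure this.

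At stake is the primary comparison of Schnozzle with the marketed dilators and unaided breathing. The point is confined to visit 1 PNIF. It does not cover the home forms or the NOSE scores, which the text does not tie to the five-minute check.

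**Working it through.** **The plan's own figures.** Section 7c gives n = 30 at 80% power and alpha 0.05, 35 recruited per cohort and 5 lost.

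- 35 − 5 = 30 and 2 × 35 = 70, so the attrition step is consistent (5/35 = 14.3%).
- The 30 itself cannot be reproduced, because no PNIF difference, SD or within-person correlation is given.
- Back-solving 30 as a paired, two-sided comparison (an assumption) gives d = (1.960 + 0.842)/√30 = 0.51 SD by the normal approximation, or 0.53 SD by the noncentral t. The 0.53 is used below for illustration only.

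**Complete rows.** Let q be the chance that a given device yields no PNIF in a given person. It is assumed equal and independent across devices; the documents give no value. Then P(all six measured) = (1 − q)^6.

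The q that uses up the whole allowance solves (1 − q)^6 = 30/35, so q = 1 − (30/35)^(1/6) = 0.025.

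The table takes 35 people with nasal valve collapse. Power is for a paired contrast at 0.53 SD, with n rounded.

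| q | P(all six) | Complete rows of 35 | Power, complete rows | With a reading on one device | Power, that device vs unaided |
|---|---|---|---|---|---|
| 2% | 0.886 | 31.0 | 0.81 | 34.3 | 0.85 |
| 5% | 0.735 | 25.7 | 0.74 | 33.2 | 0.84 |
| 10% | 0.531 | 18.6 | 0.59 | 31.5 | 0.83 |
| 20% | 0.262 | 9.2 | 0.29 | 28.0 | 0.77 |

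A contrast between two devices needs both readings: 35 × (1 − q)^2 = 31.6 at 5% and 28.4 at 10%. Most of the loss in the complete-row columns therefore comes from demanding all six readings, not from the readings actually missing.

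A participant removed at a random position from 1 to 6 has completed on average (0 + 1 + 2 + 3 + 4 + 5)/6 = 2.5 device readings plus the unaided one. A complete-row analysis discards all of them.

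**Available cases.** Let g be the gap in true PNIF gain between those who tolerate a device and those who do not, in SD units (also assumed). The mean in tolerators minus the mean in everyone is q × g:

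- g = 0: no bias at any q.
- g = 0.5 to 1 at q = 5%: 0.025 to 0.05 SD.
- g = 0.5 to 1 at q = 20%: 0.10 to 0.20 SD.

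For scale, with 33 people the standard error of a mean gain is about 1/√33 = 0.17 SD. The documents fix neither q nor g, so neither the size nor the sign of the bias can be derived from them.

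**The case against.** A reader might infer that a device failing the five-minute check gets no PNIF, so that each device's primary result is averaged only over those who tolerate it and its gain is overstated. The documents do not support that:

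- Section 4a does not say the reading is withheld after a failed check. The five minutes also serve for adjustment, and testing of all six devices is stated without exception. Missing readings follow from refusal or removal, not from the check itself.
- A device that does not fit is mentioned nowhere. Fitting follows manufacturer recommendations, and unsuitable anatomy is excluded in section 5.
- Averaging over tolerators assumes an available-case analysis, which section 7c does not specify.
- The background remark on marketed products, "they are typically described as uncomfortable and carry social stigma", goes on to concern extended use. It says little about five minutes in clinic.
- Section 8a expects discomfort to be infrequent, so per-device rates of 10% or 20% are only outer illustrations. Section 7d would also halt the study if many participants could not finish for comfort reasons.
- Section 7a defines PNIF in use, and comfort is a separate secondary outcome. Counting intolerance as zero gain is a choice of estimand, so the in-use mean is not wrong in itself.
- People for whom the dilators do not work are a different case: "These subjects will not be excluded but may leave the study".

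Two further objections have weight. The study is a pilot and the ANOVA is conditional. Also, some of the 5 expected losses may be people who never return after visit 1, whose PNIF readings would be complete; this would leave more of the allowance for losses within the session.

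All of this limits the claim about bias. It does not answer the gap: refusal and removal are written into the protocol, the primary outcome assumes they do not happen, and no rule connects the two.

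**Conclusion.** The point holds as an unhandled gap in the primary analysis, not as a demonstrated bias.

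- **Precision.** This is the firmer part, but it applies only if the ANOVA is run on complete rows. Under equal, independent losses, about 2.5% per device consumes the whole 5-of-35 allowance. At 5%, about 26 of 35 remain, and illustrative power falls from 0.80 to about 0.74. Infrequent discomfort is enough to matter, because six devices compound it.
- **Bias.** If available cases are used, devices may be compared on different, tolerance-selected groups. The effect is probably small given the protocol's own expectation about discomfort. A claim that the worse-tolerated device is favoured would need non-tolerators to gain less, which the documents do not establish.

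The loss rates, their independence, the gap g and the 0.53 SD effect are all assumptions.

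**What to change.** In section 7c:

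1. Replace the ANOVA with a linear mixed model for PNIF (device fixed, participant random) that uses every reading taken, including those from participants who refused a device or were later removed. This recovers the discarded readings. It does not by itself remove selection on tolerance, which is why items 2 and 3 are needed.
2. Record and report, for each device, the number due to be fitted and the number with no PNIF, with the reason (discomfort, refusal, removal or other). The reason has to be captured at the session, so the form should be settled before data collection.
3. Add a supportive sensitivity analysis in which a device not tolerated takes that participant's own unaided PNIF, meaning no gain. Report it beside the in-use result, not as a condition for claiming an advantage. The unaided reading always comes first, so any practice effect would enter the substituted value; say so in the report.

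The cost is one tick-box per device, a few sentences in 7c and a little more analysis. The sensitivity estimate will be slightly smaller for poorly tolerated devices. No extra participants, visits or measurements are needed, and no change to when a device or participant is stopped is proposed.

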### 2. Objectives (include all primary and secondary objectives)

#### *Primary objective:*

Determine the effectiveness of the Schnozzle nasal dilator compared to existing nasal dilator products and a control (unaided breathing) using objective peak nasal airflow (PNIF) measurements and the Nasal Obstruction Symptom Evaluation (NOSE) instrument.

*Secondary objective:*

Determine the comfort, inconspicuousness, usability, overall patient satisfaction, device compliance, sizing, pricing, and other patient perception of the nasal dilator products.

**3. Background** (*briefly describe pre-clinical and clinical data, current experience with procedures, drug or device, and any other relevant information to justify the research*)

Mechanical nasal obstruction is one of the most common complaints heard by otolaryngologists every day [3]. In fact, over 73% of the population experiences continually elevated inspiratory resistance as a result of obstructed nasal airflow [4]. In patients seeking treatment, the primary causes of nasal obstruction are chronic inflammation due to allergies (38%) and permanent structural abnormalities (62%) [9]. While the inflammatory causes of nasal obstruction are generally well controlled with topical and systemic pharmacotherapy, the structural impediments to airflow must be treated through mechanical alteration of these flow-limiting segments [10].

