## **5. Inclusion/Exclusion Criteria**

Subjects will be recruited from patients who have presented to Otolaryngology clinics with complaints of nasal obstruction. Specifically, patients who have been found to have nasal valve collapse by an Otolaryngologist based on performance of the Cottle maneuver will be invited to participate in the study. Additionally, participants will be evaluated for inclusion in the same manner if they were recruited utilizing flyers, social media, or discovered our study via the clinicaltrials.gov website. They will be excluded if after examination they are determined by their Otolaryngologist to be unsuitable or unsafe for an internal nasal dilator (e.g. history of granulomatosis with polyangiitis, extensive prior sinus or turbinate surgery altering nasal cavity anatomy, pre-existing mucosal injuries or abnormalities). Included participants will then be asked to complete the survey, NOSE questionnaire, and testing session either at the same visit or on another visit depending on patient and tester availability. Additionally we will include a control arm whom do not have evidence of nasal valve collapse, but are willing to participate in the study. Members of the control arm will also be excluded if they are deemed unsuitable based on nasal anatomy and/or the above exclusion criteria listed above.

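### Unaided PNIF is always the first test, so device-versus-unaided is an uncontrolled before-after comparison and not a placebo or non-treatment arm

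*Combined protocol and SAP*

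**What the plan says.** Section 2 (primary objective) sets out to measure Schnozzle "compared to existing nasal dilator products and a control (unaided breathing"), on PNIF and NOSE.

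Section 4a starts the clinic session with the unaided reading: "Patients will then be asked to inhale rapidly into an airflow transducer to measure baseline peak nasal inspiratory flow (PNIF"). The devices follow, each with five minutes of use before its PNIF test, and "the order of fitting nasal dilators will be randomized". Section 4b gives the same sequence for the first visit: "one to begin the study with baseline PNIF measurements, device fitting, PNIF with each device in place". Of the second visit it says: "This will be followed up with a wrap up visit end the study with a concluding survey". No PNIF test is described there.

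Section 7a times the primary outcomes before the trial and during use of each device, with no later unaided time point. Section 4e then describes the "baseline NOSE and PNIF score from participants without any assistive devices in place, which serves as the placebo/ non-treatment arm of the study".

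Section 5 adds a second cohort: "Additionally we will include a control arm whom do not have evidence of nasal valve collapse". Section 4a has every subject tested with all six devices, and no section exempts this cohort. Section 7c makes statistical testing conditional, names ANOVA at p < 0.05, and specifies no model terms.

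**The concern.** In a crossover, randomising the order of conditions is what separates condition from test position. Here six of the seven PNIF conditions are in the random order, and the seventh, unaided breathing, is fixed in first place. If people blow differently on a first attempt than on later ones, through practice, fatigue or changed effort, that difference is counted as device effect. It can create a benefit or hide one.

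For NOSE the unaided score is also described only before the devices. If device NOSE scores come from the home surveys, the contrast mixes device with elapsed days and with the move from clinic to home. The appendices were not supplied, so this part is conditional.

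The label matters because a reader told that there is a non-treatment arm will take the unaided contrast as controlled. That contrast is in the primary objective, and Section 9a says that the trial will supply clinical evidence for redesign.

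**Working it through.** **Inputs.** Section 7c: 30 patients with collapse, alpha 0.05, power 80%. Section 4a: six devices, random order, unaided first. Not given: effect size, SD, sidedness, efforts per PNIF test, size of any drift. Assumed: a two-sided paired t test, so 2.5% in the improvement direction. Effects are in SDs of the paired difference.

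**The plan's own figure.** The attrition arithmetic holds: 35 − 5 = 30 per cohort and 2 × 35 = 70. The 30 itself cannot be reproduced without an effect size and SD. At n = 30 and 80% power, the detectable paired difference is (1.960 + 0.842)/√30 = 0.51 SD by the normal approximation, or 0.53 by the t distribution.

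**Can the contrast be estimated?** Take 30 subjects × 7 readings with subject, condition and test-position terms.

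| Design and position term | Rank / parameters | Device − unaided |
|---|---|---|
| Planned, position as factor | 41 / 42 | not estimable |
| Planned, linear position | 37 / 37 | estimable only through the assumed line |
| Unaided in the random order, position as factor | 42 / 42 | estimable |

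Device-minus-device is estimable in all three. Random device order therefore lets a smooth trend across the six device tests be estimated and extrapolated back to baseline. It gives no information on a step between the baseline test and the first device test.

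**Size if a step exists (assumed).** With no true effect, the chance of a significant improvement is P(T > t₀.₉₇₅,₂₉), where T is noncentral t with noncentrality step × √30:
- 0.1 SD: 7.6%
- 0.2 SD: 18%
- 0.5 SD: 75%

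For a step in the opposite direction, the noncentrality is (effect − step) × √30:

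| True effect | No step | 0.1 | 0.2 | 0.5 |
|---|---|---|---|---|
| 0.53 SD | 80% | 62% | 41% | 4% |
| 0.8 SD | 99% | 96% | 89% | 36% |
| 1.0 SD | >99% | >99% | 99% | 75% |

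**Does a linear order term rescue the planned data?** In simulation (2,000 trials per cell, pooled-error ANOVA, no true effect, average drift 0.5 SD), adding it cut false improvement from 74% to 2% for linear drift, from 78% to 31% for a saturating learning curve, and from 78% to only 65% for a first-test step. It also raises the SE from √(1/30) = 0.183 to about 0.21.

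**Unaided in the random order.** With free period terms the SE is 0.186. False improvement was 2.0% to 3.0% in every drift scenario simulated.

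**Carryover, the price of that design.** Six of seven randomised unaided readings follow a device. Assume 20% carryover, a true effect of 0.53 SD and equal effects for all devices.
- Carryover into unaided readings only: the randomised contrast is 0.529 × (1 − 0.2 × 6/7) = 0.44 and the baseline contrast 0.53. The randomised one is less biased only if the first-test step exceeds 0.529 × 0.2 × 6/7 = 0.09 SD.
- Carryover into all readings: the randomised contrast is 0.529 × (1 − 0.2/7) = 0.51 and the baseline contrast 0.529 × (1 + 0.2 × 5/6) = 0.62.

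**The case against.** Several objections have force.

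- **It is a pilot.** Section 7c aims at needs and preferences, and testing may never be done. That stands, and the error rates apply only if the ANOVA is run. The same bias still sits in a descriptive mean difference.
- **The marketed devices are a benchmark.** They share the random order, so a common first-test step cannot make Schnozzle look better than they do. That stands in full. A reader might infer that the crossover as a whole is confounded, but the random device order does not support that.
- **The wording is thin evidence.** Section 4e answers a fixed form prompt, and its sentence says that the scores are baseline and without devices. A careful reader can see the before-after structure, which limits the harm but does not make the label accurate. Likewise, the absence of an order term says little, because Section 7c specifies no terms at all.
- **The power losses rest on one effect size.** The 0.53 SD is back-solved from n = 30, and at 0.8 or 1.0 SD small reverse steps cost little, as the table shows.
- **Randomising unaided breathing exchanges one unknown bias for another.** That is fair, since no washout is described. It is a reason to keep the baseline and to name the lead contrast in advance.

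Two defences fail. Random device order does not reach the baseline step. The cohort without collapse is not an untreated time control, because nothing exempts it from the devices. Comparing before-after change between cohorts would assume equal drift and would estimate only the extra benefit in collapse.

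**Conclusion.** The point holds as a matter of design. For PNIF, device-versus-unaided is an uncontrolled before-after comparison, and a first-test step cannot be told apart from a device effect without an assumption that these data cannot check. Section 4e claims a control that the design does not contain.

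A reader might go further and infer that a drift is present, or that the unaided results will be falsely positive. The documents do not support that: they give no size or direction for any step, and every rate above rests on an assumed one. Nor do they support treating NOSE as equally affected while the source of the device NOSE scores is unknown. Severity is minor to moderate, and mainly a matter of interpretation.

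**What to change.** **Minimum (wording only).** In Section 4e, replace the arm label with *device-free baseline*. In Section 7c, state that device-versus-unaided results for PNIF and NOSE are uncontrolled before-after comparisons. If the ANOVA is run on the planned data, any sensitivity analysis for order must use a linear trend in test position. Position as a factor leaves the contrast not estimable, and software may still print an arbitrary number. The report must also say that the trend gives little protection against a first-test step.

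**Cheap improvement for PNIF.** Keep the baseline and add one unaided PNIF test to each participant's random order, with the same five-minute interval and number of efforts as for a device. Analyse the seven randomised readings with subject, period and condition terms. Name the randomised unaided contrast in advance as the lead one, and report the baseline contrast as a sensitivity analysis. The before-after statement in Section 7c would then apply to the baseline contrast and to NOSE.

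**Cost.** About five minutes and one more test per participant, and a new randomisation list, with no extra visit and almost no loss of precision. The drawback is possible carryover into the unaided readings, quantified above. Participants still know when they wear no device, so expectation effects remain, and NOSE stays before-after.
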